The number and percentage of participants experiencing solicited post-vaccination reactogenicity (fever, diarrhea, vomiting, decreased appetite, irritability, decreased activity level) during the 7-day period after each vaccination will be tabulated by vaccine group and severity. For the percentage, an exact two-sided 95% CI will be provided using Clopper-Pearson method.

The percentage of participants with at least one solicited post-vaccination reactogenicity between ROTAVIN and ROTAVIN-M1 groups after each vaccination will be compared using a two-sided Fisher's Exact test with a significance level of 0.05.

12.4.3 12.4.3 Analysis of secondary objectives

Analysis of secondary immunogenicity objectives

The percentage of participants with seroconversion and seropositivity 28 days after the second vaccination will be computed for the ROTAVIN and ROTAVIN-M1 groups along with exact two-sided 95% CIs based on Clopper-Pearson method. The difference in the percentage between the two groups will be provided along with its two-sided 95% CI obtained by Miettinen and Nurminen method.

In addition, a reverse cumulative distribution (RCD) curve for anti-rotavirus IgA concentrations will be created by vaccine group and visit.

Analysis of secondary safety objectives

The number and percentage of participants experiencing immediate adverse events within 30 minutes after each vaccination, unsolicited AEs four weeks after each vaccination and SAEs including intussusception reported through 4 weeks after the last vaccination will be provided by vaccine group, severity, and causality. For the percentage, an exact two-sided 95% CI will be provided using Clopper-Pearson method.

The original verbatim terms used by investigators to identify adverse events on case report forms (CRFs) will be coded according to MedDRA dictionary. AEs including SAEs will be summarized and classified by SOC and preferred term of the MedDRA dictionary. They will be displayed by vaccine group as both frequencies and percentages.

The analysis of unsolicited adverse events comprises the following categories:

- Any unsolicited AEs;
- Related unsolicited AEs;
- SAEs;
- Related SAEs;
- Unsolicited AEs leading to withdrawal from the study;
- Unsolicited AEs leading to withdrawal from study vaccination but remaining in the study;
- Unsolicited AEs leading to hospitalization;

• Any AEs leading to death.

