All reported AEs that start after vaccination will be tabulated. If a given disease is already reported as ongoing at the first visit on the medical history pages, it will be counted and tabulated as a vaccine emergent adverse event only if it worsens after the immunization with the study vaccine. When an adverse event occurs more than once for a participant, the maximal severity and strongest relationship to the vaccine group will be counted.

SAEs and discontinuation due to AE(s) will be described in detail by vaccine group.

Data listings of all adverse events will be provided by participant.

The medications taken during study period will be coded using WHO DD. The concomitant medications will be tabulated by ATC classification and preferred drug name of WHO DD for each vaccine group.

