13.2.2 Unsolicited Adverse Events (AEs)

Solicited reactions that occur within 7 days after any study vaccination are recorded in the PIDC Reconciliation: Reactogenicity Form. Solicited reactions that become SAEs, i.e. participant was hospitalized, need to be recorded in the Serious Adverse Event Report Form. To trigger the Serious Adverse Event Report Form, the Adverse Event Form must be filled out first, which results in the solicited reactions, that become a SAE within 7 days after any study vaccination, recorded twice as a solicited reaction and an unsolicited reaction. To avoid double counting these events, they will be summarized in tables relating to solicited reactions and SAEs but not in unsolicited adverse event tables. All other reported AEs that start after vaccination and are within four weeks after each vaccination will be tabulated. If a given disease is already reported as ongoing at the first visit on the medical history pages, it will be counted and tabulated as a

vaccine emergent adverse event only if it worsens after the immunization with the study vaccine. When an adverse event occurs more than once for a participant, the maximal severity and strongest relationship to the vaccine group will be counted.

The number and percentage of participants, and total number of events, with unsolicited adverse events within four weeks will be tabulated after any dose and after each dose for each vaccine group and overall by system organ class, preferred term, and severity (Table 29-21) and by system organ class, preferred term, and relationship with study vaccine (Table 32-34). Results will be tabulated for the safety population. For the percentage, an exact two-sided 95% CI will be provided using Clopper-Pearson method.

The number and percentage of participants experiencing unsolicited AEs will be summarized after any dose and after each dose by MedDRA system organ class and preferred term (Table 35-37). This summary will be repeated for related unsolicited AEs, unsolicited AEs leading to withdrawal from the study, and unsolicited AEs leading to withdrawal from study vaccination but follow-up continued (Tables 38-42). Results will be tabulated for the safety population for each vaccine group and overall.

Unsolicited AEs by MedDRA system organ class will be presented by relationship to study vaccine (Figure 9) and severity (Figure 10) for each vaccine group.

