13.2.3 Serious Adverse Events (SAEs)

The number and percentage of participants, and total number of events, with SAEs including intussusception reported through 4 weeks after the last vaccination will be tabulated after any dose and after each dose for each vaccine group and overall by system organ class, preferred term, and severity (Table 43-45) and by system organ class, preferred term, and relationship to study vaccine (Table 46-48). Results will be tabulated for the safety population. For the percentage, and exact two-sided 95% CI will be provided using Clopper-Pearson method.

The number and percentage of participants experiencing SAEs including intussusception reported through 4 weeks after the last vaccination will be summarized after any dose and after each dose by MedDRA system organ class and preferred term (Table 49-51). This summary will be repeated for related SAE, and unsolicited AEs leading to hospitalization and deaths (Tables 52-56). Results will be tabulated for the safety population for each vaccine group and overall.

All SAEs will be listed (Listing 17).

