E terminology will not be included in this table

Table 41: Unsolicited AEs Leading to Withdrawal from the Study by System Organ Class and Preferred Term – Safety Population

{This table will be similar to Table 35}

Programming Note: The SOCs will be ordered starting with the most common SOC.

Table 42: Unsolicited AEs Leading to Withdrawal from the Study Vaccination but Follow-up Continued by System Organ Class and Preferred Term – Safety Population

{This table will be similar to Table 35}

Table 43: SAEs by System Organ Class, Preferred Term, Vaccine Group, and Severity – Safety Population – After Any Dose

{This table will be similar to Table 29}

Programming Note: The SOCs will be ordered starting with the most common SOC.

Table 44: SAEs by System Organ Class, Preferred Term, Vaccine Group, and Severity – Safety Population – After Dose 1

{This table will be similar to Table 29}

Programming Note: The SOCs will be ordered starting with the most common SOC.
E terminology will not be included in this table

Table 45: SAEs by System Organ Class, Preferred Term, Vaccine Group, and Severity – Safety Population – After Dose 2

{This table will be similar to Table 29}

Programming Note: The SOCs will be ordered starting with the most common SOC.
E terminology will not be included in this table

Table 46: SAEs by System Organ Class, Preferred Term, Vaccine Group, and Relationship with study vaccine – Safety Population – After Any Dose

{This table will be similar to Table 32}

Programming Note: The SOCs will be ordered starting with the most common SOC.

Table 47: SAEs by System Organ Class, Preferred Term, Vaccine Group, and Relationship with study vaccine – Safety Population – After Dose 1

{This table will be similar to Table 32}

Programming Note: The SOCs will be ordered starting with the most common SOC.
E terminology will not be included in this table

Table 48: SAEs by System Organ Class, Preferred Term, Vaccine Group, and Relationship with study vaccine – Safety Population – After Dose 2

{This table will be similar to Table 32}

Programming Note: The SOCs will be ordered starting with the most common SOC.
E terminology will not be included in this table

Table 49: SAEs by System Organ Class and Preferred Term – Safety Population – After Any Dose

{This table will be similar to Table 35}

Programming Note: The SOCs will be ordered starting with the most common SOC.

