Table 50: SAEs by System Organ Class and Preferred Term – Safety Population – After Dose 1

{This table will be similar to Table 35}

Programming Note: The SOCs will be ordered starting with the most common SOC.
E terminology will not be included in this table

Table 51: SAEs by System Organ Class and Preferred Term – Safety Population – After Dose 2

{This table will be similar to Table 35}

Programming Note: The SOCs will be ordered starting with the most common SOC.
E terminology will not be included in this table

Table 52: Related SAEs by System Organ Class and Preferred Term – Safety Population – After Any Dose

{This table will be similar to Table 35}

Programming Note: The SOCs will be ordered starting with the most common SOC.

Table 53: Related SAEs by System Organ Class and Preferred Term – Safety Population – After Dose 1

{This table will be similar to Table 35}

Programming Note: The SOCs will be ordered starting with the most common SOC.
E terminology will not be included in this table

Table 54: Related SAEs by System Organ Class and Preferred Term – Safety Population – After Dose 2

{This table will be similar to Table 35}

Programming Note: The SOCs will be ordered starting with the most common SOC.

E terminology will not be included in this table

Table 55: Unsolicited AEs Leading to Hospitalization by System Organ Class and Preferred Term – Safety Population

{This table will be similar to Table 35}

Programming Note: The SOCs will be ordered starting with the most common SOC.

Table 56: Deaths by System Organ Class and Preferred Term – Safety Population

{This table will be similar to Table 35}

Programming Note: The SOCs will be ordered starting with the most common SOC.

Table 57: Overall Safety Summary: Adverse Events – Safety Population

	ROTAVIN x (%)		ROTAVIN-M1 x (%)		Total x (%)	
	No. of Participants ^a	No. of Events ^b	No. of Participants ^a	No. of Events ^b	No. of Participants ^a	No. of Events ^b
Total Number of Participants Enrolled	xx	xx	xx	xx	xx	xx
Total Number of Participants receiving Dose 1	xx	xx	xx	xx	xx	xx
Total Number of Participants receiving Dose 2	xx	xx	xx	xx	xx	xx
Total Number of Vaccinations	xx	xx	xx	xx	xx	xx
Total Number of Participants in the Safety Population	xx	xx	xx	xx	xx	xx
Total Number of Events^c	x (x)	xx	x (x)	xx	x (x)	xx
Total Immediate Adverse Events – After Any Dose	x (x)	x (x)	x (x)	x (x)	x (x)	x (x)
Severity						
Mild	x (x)	x (x)	x (x)	x (x)	x (x)	x (x)

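### Tables 41 and 42 count only unsolicited AEs, so a non-serious Day 1-7 solicited reaction that ends participation or prevents Dose 2 is in neither

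*SAP*

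**What the plan says.** **Recording.** SAP 13.2.2 states: "Solicited reactions that occur within 7 days after any study vaccination are recorded in the PIDC Reconciliation: Reactogenicity Form". The Adverse Event form is described as necessary for such a reaction only when it becomes an SAE, because that form opens the SAE form. To avoid counting these serious cases twice, the SAP decides that "they will be summarized in tables relating to solicited reactions and SAEs but not in unsolicited adverse event tables". Protocol 9.7 adds that a solicited symptom that starts within seven days and continues past Day 7 is still reported as reactogenicity. Protocol 9.4 treats every solicited reaction in that window as related to vaccine.

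**Tabulation.** Tables 41, 42 and 55 are all restricted to unsolicited AEs, in the SAP text (13.2.2 and 13.2.3) and in the shells. Table 42 reads "Unsolicited AEs Leading to Withdrawal from the Study Vaccination but Follow-up Continued by System Organ Class and Preferred Term", and the hospitalisation shell reads "Table 55: Unsolicited AEs Leading to Hospitalization by System Organ Class and Preferred Term". The restriction comes from the category list in Protocol 12.4.3, for example "Unsolicited AEs leading to withdrawal from study vaccination but remaining in the study". The same protocol section also promises that "SAEs and discontinuation due to AE(s) will be described in detail by vaccine group", without confining this to unsolicited events.

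**The concern.** Tables 41 and 42 are where a reader looks to see whether any adverse event stopped an infant's vaccination or participation. The six solicited terms are the reactions expected from a live oral rotavirus vaccine. They form the primary safety endpoint and are related by protocol rule. If one of them leads a parent to decline Dose 2 or leave the study, these tables do not count it. A zero in Table 41 or 42 could then be read as no treatment-limiting reactions, when the tables were not built to count the most likely kind. Table 55 has a related labelling problem: it is the only table presented as the hospitalisation summary, yet the counting rule removes hospitalised solicited reactions from it.

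**Working it through.** The plan gives no figure to reproduce. The check follows three hypothetical infants from form to table.

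| Case | Form under the SAP rule | Table expected to show it | Counted there? | Where it does appear |
|---|---|---|---|---|
| A. Non-serious solicited reaction after Dose 1; Dose 2 not given; follow-up continues | Reactogenicity form | Table 42 | No: solicited, not unsolicited | Generic reason in Table 1 and Table 58; reason in Listing 19; the reaction itself in Listing 11 (Listing 13 if severe) |
| B. Non-serious solicited reaction; infant leaves the study | Reactogenicity form | Table 41 | No: same reason | Reason in Table 1 and Listing 1; the reaction in Listing 11 or 13 |
| C. Solicited reaction on Day 3; infant hospitalised | Reactogenicity, AE and SAE forms | Table 55 | No: removed by the 13.2.2 rule | SAE Tables 43-51 (52-54 if related); Listings 15 and 17 |

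**Cases A and B.**
- The solicited tables (16-18 and 59-64) give severity, onset, duration and ongoing status. None has a row for withdrawal or discontinuation, and neither does the overall summary, Table 57.
- Table 58 offers one undifferentiated entry for a reaction to the previous dose. Table 1 gives disposition reasons. Neither names the event.
- Listing 1 covers early study terminations (SAP 8.1), so case A is not in it at all. For an adverse-event termination it prints the preferred term from the Adverse Event form, where the SAP does not require a non-serious solicited reaction to be entered.
- The protocol provides real routes to these cases. Section 7.4 lets a parent decline further vaccination and stay in follow-up. Section 5.1.3 bars further doses if an exclusion criterion appears during dosing, and criterion 15 is diarrhoea lasting 14 days or longer. Such diarrhoea starting in Days 1-7 would remain solicited under Protocol 9.7.

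**Case C.** Inpatient hospitalisation makes an AE serious (Protocol 9.9). The event is therefore shown by system organ class, preferred term, arm, severity and relationship in the SAE tables. Listing 17 also prints the seriousness criterion. Only the agreement between Table 55 and Listing 17 fails.

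**Possible size.** The documents give no rate at which solicited reactions stop vaccination. A ceiling for Table 42 is the number of infants with any solicited reaction after Dose 1. Protocol 2.5.3 reports about 5% among ROTAVIN-M1 recipients in the earlier phase III study. Assuming that rate in both arms, 0.05 × 550 = 27.5 and 0.05 × 275 = 13.75, or about 41 infants. Over the 1% to 20% range in Protocol Table 12.2, the ceiling is 0.01 × 825 = 8 to 0.20 × 825 = 165. The infants who actually stop would be an unknown and probably small fraction of these.

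**The case against.** The strongest reply is that little is lost.

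- **Hospitalisations are fully reported.** A reader might infer from Table 55 that an infant hospitalised with a solicited reaction disappears from the report. The documents do not support that, because the SAE tables and Listing 17 carry every such case. Table 55 is also specified in the SAE section (13.2.3), so it could be argued to be an SAE table that the exclusion does not reach. Its title and text say unsolicited, so this is at least an ambiguity to settle.
- **Not every solicited case is excluded.** The 13.2.2 exclusion names reactions that become serious within seven days. One that turns serious later falls outside it. Under Protocol 7.1, clinically significant findings from an immediate reaction are reported as unsolicited AEs. Some such cases may reach the tables.
- **Form content is not visible.** The documents do not say what a site enters when a non-serious solicited reaction ends participation. Listing 1's programming note suggests an AE entry may be expected. If one is made, 13.2.2 does not exclude it. This stands as a limit, but it also means the counts in Tables 41 and 42 would depend on an unstated data-entry practice.
- **Discontinuations can be traced.** Table 1, Table 58 and Listings 11, 13 and 19 together allow a reader to find the named reaction, and Protocol 12.4.3 promises a description. This is true, but it needs record-by-record cross-reading, and no SAP table by event term delivers that description for solicited reactions.
- **The scope was deliberate.** The protocol list is introduced as the analysis of unsolicited AEs. That explains the restriction but does not fill the gap, since no parallel summary exists for solicited reactions.

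**Conclusion.** The point holds for Tables 41 and 42: as written, a non-serious solicited reaction with onset in Days 1-7 that ends participation, or after Dose 1 prevents Dose 2, is counted in neither. This assumes that such reactions are recorded only on the reactogenicity form, as the SAP describes. For Table 55 the defect is narrower: an incomplete table that would not agree with Listing 17, with the events fully reported elsewhere.

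Two stronger readings should be avoided. A reader might count the seven-day windows after both doses as feeding Table 42, but with a two-dose schedule only the window after Dose 1 can lead to a missed dose. A reader might also attach an upper confidence limit to a zero in these tables, but they follow the Table 35 shell, which has no interval.

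The number of infants affected is likely small. In the earlier phase III study the commonest solicited events were each below 3%, and all three SAEs came more than 40 days after vaccination. No primary estimate, test, population or sample size changes. This is a cheap improvement to safety reporting and does not threaten the trial's conclusions.

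**What to change.** 1. Define Tables 41 and 42, and the matching bullets in Protocol 12.4.3, on all AEs leading to study withdrawal or vaccine discontinuation, whether solicited or unsolicited. Count each event once, which also meets the SAP's concern about double counting. Where the reactogenicity form does not record the consequence, link it through the recorded reason for termination or for the dose not given.
2. In Listing 1, print the solicited term when a solicited reaction is the reason.
3. For Table 55, either include solicited reactions that became SAEs and retitle it, or add a footnote saying that they are excluded and pointing to the SAE tables and Listing 17.

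The cost is SAP, shell and protocol wording plus a merge of forms already planned for the database. No new data are collected. The counts in these tables can only stay the same or become slightly less favourable.

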- 2. Study staff will make a physical home visit on Days 58 (+1 day) and Day 64 (+2 day) and a telephone call to the participant's parent/LAR on Day 61 (+2) to determine the child's health status and to support completion of the PIDC. In case the child experiences any illness during this period, they will be referred to the study clinic for further evaluation and treatment.
- 3. Completed PIDC can be collected by the field officer at on Day 64 visit or the parent can bring it to the site at the next visit, if parents were not available during the home visit.
- 4. The parent/LAR will be instructed that if the participant later experiences an AE requiring medical care, the parent should inform the investigator as soon as possible and seek medical care as appropriate. If the participant visits a health care provider, the participant parent/LAR should be sure to inform the health care provider of participation in this study and give the health care provider the contact information for the investigator.
- 5. The data in the PIDC collected by the parents will be reviewed by the study physician/designee and entered in the CRF. Any solicited reaction extending beyond 7 days after vaccination will also be recorded on the PIDC/CRF with date of resolution (if available) and the highest severity during the occurrence. Also, unsolicited AEs will be captured up to 28 days after each vaccination and SAEs including suspicion of intussusception will be recorded at all times between first vaccination and last visit. These will be managed medically as needed.

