9 ASSESSMENT OF SAFETY AND ADVERSE EVENTS

9.1 Adverse Events

Adverse Event: An adverse event is defined as any untoward medical occurrence in a participant after administration of the investigational vaccine and that does not necessarily have a causal relationship with the investigational vaccine. An AE can therefore be any unfavourable and unintended sign (including abnormal laboratory findings), symptoms, physical examinations, or

disease temporally associated with the use of the investigational vaccine, whether or not related to the investigational vaccine. This definition includes exacerbations of pre-existing conditions. Stable pre-existing conditions which do not change in nature or severity during the study are not considered AEs; however, these should be reported as part of the medical history. AE's will be recorded from D1 after study vaccination up to last visit of the participant. An AE does not include:

- Medical or surgical procedures (e.g., surgery, endoscopy, transfusion), but the condition that leads to the procedure is an AE.
- Situations where an untoward medical occurrence has not occurred (e.g., hospitalization for elective surgery, social and / or convenience admissions).
- Overdose of either study drug or concomitant medication without any signs or symptoms

Information to be collected on AEs includes event description, time of onset, clinician's assessment of severity, relationship to study product, and time of resolution/stabilization of the event. AE assessment should be made only by those with the training and authority to make a diagnosis.

Solicited AEs are pre-specific adverse events that are common or known to be associated with vaccination and that are actively monitored as indicators of vaccine reactogenicity. Investigators will not be required to assess causality of solicited adverse events if the onset is during the solicitation periods. Solicited adverse events with onset after the solicitation period will be captured as unsolicited AEs.

For this trial, immediate AEs will be assessed by study staff 30 minutes after each vaccination and solicited AEs will be assessed daily for 7 days after each vaccination by the participants. Participant parent/LAR will be provided a diary to record the presence or absence of solicited AEs, severity of the solicited AE and use of concomitant medication.

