9.2 AE/SAE Reporting Period and Parameter

The safety profile will be evaluated by the proportion of participants experiencing AEs, related or not related, under the following five categories:

- Number and percentage of participants with immediate adverse events within 30 minutes after each vaccination.
- Number and percentage of participants with solicited adverse events (fever, diarrhea, vomiting, decreased appetite, irritability, and decreased activity level) over the 7-day period (Days 1-7) post vaccination.
- Number and percentage of participants with unsolicited adverse events from first vaccination through four weeks after the last vaccination (Unsolicited adverse events are any untoward

medical occurrence in the participant, temporally related to receipt of the study products, whether or not considered related).

• All serious adverse events (SAEs) and Intussusception from first vaccination through four weeks after the last vaccination.

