9.8 Unsolicited Adverse Events

Unsolicited adverse events are any AEs that occur any time after the study vaccine is given (temporally related to study product), whether or not deemed "related" to the product, and are not solicited. Unsolicited AEs can be observed by study staff while the participant is at a clinic for a study visit or reported by the participant's parent/LAR at any time. Unsolicited adverse events will be recorded with onset from the time of vaccination up to 28 days after each vaccination. Any solicited sign or symptom starting after 7 days post vaccination will be recorded as an "unsolicited AE".

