All SAEs reported from the time of first vaccination upto 4 weeks after last vaccination will be reported in the study. All SAEs must be reviewed and evaluated by a study clinician (SAE relationship to study vaccine must be evaluated as outlined in Section 9.4) and recorded on an SAE form and reported, as specified in Section 9.1010. All such SAEs should also be followed until satisfactory resolution or until the investigator deems the event to be chronic or the patient to be stable.

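### The documents conflict on the unsolicited-AE window and, read literally, SAP 13.2.2 leaves non-serious events outside the 28-day windows out of Tables 38–42, including any that stopped vaccination

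*SAP*

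**What the plan says.** The protocol gives two kinds of window for unsolicited AEs.

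- **Continuous.** Under 9.1, AEs "will be recorded from D1 after study vaccination up to last visit of the participant". Section 9.5 likewise has all AEs and SAEs entered in the eCRF throughout participation. Section 9.2 counts "unsolicited adverse events from first vaccination through four weeks after the last vaccination". A sentence in 12.4.3, under the secondary safety analysis, reads "All reported AEs that start after vaccination will be tabulated".
- **Per dose.** Section 9.8 reads "Unsolicited adverse events will be recorded with onset from the time of vaccination up to 28 days after each vaccination", and the safety follow-up text in 7.1 and 7.2 agrees. The secondary endpoint in 3.2.2 uses four weeks after each dose. So does the lead analysis paragraph of 12.4.3, which covers "unsolicited AEs four weeks after each vaccination and SAEs including intussusception reported through 4 weeks after the last vaccination".

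SAP 13.2.2 restates the broad 12.4.3 sentence with a limit added: "All other reported AEs that start after vaccination and are within four weeks after each vaccination will be tabulated". Tables 29–37 carry that limit in their titles. Tables 38–42 are introduced as the same summary repeated, but their titles carry no limit.

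For SAEs, Protocol 7.2 says "SAEs including suspicion of intussusception will be recorded at all times between first vaccination and last visit", and 7.1 agrees. Protocol 9.9 stops sooner: "All SAEs reported from the time of first vaccination upto 4 weeks after last vaccination will be reported in the study". SAP 13.2.3 also ends its tables four weeks after the last dose, and introduces Table 55 (AEs leading to hospitalization) as a repeat of that summary. SAP 13.2.4 tabulates all deaths with no time limit.

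**The concern.** Dose 2 is due 56 to 70 days after Dose 1, so two 28-day windows cannot meet. Events starting between them are expected in the database: Visits 2 and 3 ask about AEs since the previous visit, and Listing 15 has a footnote marking events that began after the four weeks.

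Tables 38–42 are where a reader looks for events judged related and events that ended dosing or participation, by arm and preferred term. If the four-week filter applies to them, it removes the weeks just before the Dose 2 decision. The documents supply an example. A history of diarrhea lasting 14 days or longer is an exclusion criterion, and 5.1.3 lists an exclusion criterion detected during the dosing period among the reasons for giving no further dose. A non-serious episode starting on Day 32 would reach 14 days on Day 45, before Dose 2 is due. Under the literal reading it would not appear in Table 42.

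At the other end, an SAE starting 35 days after Dose 2 in an infant whose final visit is late is recorded under 7.2. It lies outside 9.9 and outside the SAE tables.

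**Working it through.** The plan gives no figure for this, so there is nothing to reproduce. The check is day arithmetic on the plan's schedule, followed by a comparison of the outputs.

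**Inputs.** Dose 1 is Day 1. Dose 2 is 56 days later with a +14-day window (Protocol 7.2), so Day 57 to Day 71. The final visit is 28 days after Dose 2 with a +14-day window (Protocol 7.3). The unsolicited-AE window is 28 days after each dose (Protocol 9.8, SAP 13.2.2).

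**Gap between doses.** The first window ends on Day 1 + 28 = Day 29.
- Dose 2 on Day 57: gap is Days 30–56, 56 − 29 = 27 days. Share of the inter-dose interval: 27/56 = 48%.
- Dose 2 on Day 71: gap is Days 30–70, 70 − 29 = 41 days. Share: 41/70 = 59%.
- If four weeks is counted as Days 1–28, the gap is 28 to 42 days.

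**Tail after Dose 2.** The final visit falls 28 to 42 days after Dose 2 and the window ends at 28 days, so the tail is 0 to 14 days.

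**Share of calendar days from Day 1 to the final visit.**

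| Dose 2 | Final visit | Gap + tail | Share |
|---|---|---|---|
| Day 57 | Day 85 | 27 + 0 = 27 | 27/85 = 32% |
| Day 57 | Day 99 | 27 + 14 = 41 | 41/99 = 41% |
| Day 71 | Day 99 | 41 + 0 = 41 | 41/99 = 41% |
| Day 71 | Day 113 | 41 + 14 = 55 | 55/113 = 49% |

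**Where an event outside the windows would appear.**
- *Non-serious AE, gap or tail.* Tables 29–37: no, by title. Tables 38–42: no under the text of 13.2.2, yes if the titles govern. Listing 15 shows it, and Listing 16 if related. Tables 1 and 58 give reasons for stopping vaccine or not giving a dose, without preferred terms. Listing 1 prints the preferred term only where an AE ended study participation.
- *SAE in the gap.* Tabulated, because SAP 13.2.3 runs continuously to four weeks after the last dose.
- *SAE in the tail.* Shown in Listing 17, outside Tables 43–54. The same cut-off applies to Table 55. A death is tabulated under 13.2.4.

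**The case against.** The best defence is that the SAP implements the pre-specified endpoint. A reader who sees only the broad sentence in 12.4.3 might infer that the protocol tabulates every AE and that the SAP departed from it. The documents do not support that: 3.2.2, 9.8 and the lead paragraph of 12.4.3 all use the SAP's window. The conflict lies within the protocol as much as between the two documents, and Tables 29–37 match the endpoint.

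A reader might also infer that events stopping Dose 2 are certain to be lost. That is not established either. The titles of Tables 38–42 carry no limit, the listings keep the events, and Tables 1 and 58 give reasons with no time limit. Table 57 states no window. Investigator-confirmed intussusception is an SAE by definition, so a case between doses is tabulated. Some grounds for withholding Dose 2, such as a household pregnancy, are not AEs at all.

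Nor do the documents show that the two sites will record different events. They share an eCRF, a manual of procedures and mandatory training, and the visit instructions ask about all AEs since the last visit.

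What stands is narrower. The text of 13.2.2 and the titles of Tables 38–42 point different ways, so two programmers could produce different tables. None of the other outputs gives incidence by arm and preferred term for events that stopped dosing. The SAP offers no reason for the added limit, although its introduction says it gives reasons for its analyses.

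**Conclusion.** The point holds in limited form. The documents give incompatible recording windows for unsolicited AEs. The SAP's rule, taken as written, omits from Tables 38–42 non-serious events starting in a gap of 27 to 41 days, or in a tail of up to 14 days. Together these make up 32% to 49% of the calendar days from Day 1 to the final visit. For SAEs only the tail of up to 14 days is affected, it is zero when the final visit is exactly 28 days after Dose 2, and deaths are not affected.

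These figures assume visits within their windows and the literal reading of 13.2.2. They measure time, not events: the documents give no rate for non-serious AEs that permanently stop Dose 2, and the upper figure needs both visits at their latest date. The primary immunogenicity and solicited-reaction analyses are untouched. The matter should be settled before database lock, because a stated rule could otherwise drop collected safety events from the tables meant to show them.

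**What to change.** 1. **Protocol.** Reconcile 7.1, 7.2, 9.1, 9.2, 9.5, 9.8, 9.9 and 12.4.3 on one recording window for unsolicited AEs and SAEs. Leave the four-week endpoint definition in 3.2.2 as it is.
2. **SAP 13.2.2.** Confine the four-week restriction to Tables 29–37. State that Tables 38–42 include all recorded unsolicited AEs with onset from first vaccination to the final visit.
3. **SAP 13.2.3.** Include all recorded SAEs, and the hospitalization events in Table 55, to the final visit, with a flag for onset more than 28 days after the last dose.

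The SAP changes cost a few sentences and a change of filter in the table programs. The protocol change touches several sections and goes through the amendment route in Protocol section 16, but the SAP changes need not wait for it. No visits are added, because Visits 2 and 3 already ask about these events. Counts in Tables 38–42 and the SAE tables may rise slightly; Tables 29–37 do not change.
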